	feasibility data will consist of calculating
	frequencies and percentages Analysis of
	questionnaires will consist of within-

group pre/post analysis with student t-test and chi square with significance will be set at .05 and two-tailed hypotheses.
Sample Size Estimation: A sample size of 25-30 participants is ideal for a pilot feasibility study ¹ . However, we are recruiting only 20 participants due to funding constraints.

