4.3 Number of Patients

Twenty participants will be enrolled. Sample size for this pilot feasibility study is determined by budgetary constraints. While a sample of 25-30 would be ideal for the aims of this study¹, we are limited by our study budget to twenty participants.

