12 STATISTICAL CONSIDERATIONS

Data will be collected via REDCap and analyzed with SPSS. Missing data will be handled with imputation of the median value of all available data for each individual item.¹⁹

Demographics: Analysis of demographic data will consist of calculating means, standard deviations, frequencies, and proportions. Demographic information to include: age, marital status, race and ethnicity, current medications and medical history.

Feasibility data: will be analyzed by calculating frequency and percentages, specifically:

- **Recruitment** frequency count (enrollment of 20 women, average of 2 eligible women per month to participate in the trial, identification of appropriate recruitment strategies, the appropriateness of eligibility criteria),
- **Retention** frequency and percentage (70% or more participants comply with 8 or more AT sessions and complete both fMRI scans)
- Safety frequency count (zero serious adverse events directly related to AT)
- **Questionnaire completion** frequency and percentage (70% or more enrolled participants complete at least 80% of questions at all protocol-directed time points).

Questionnaires: analyses will consist of student t-test and chi square computations according to the type of data.

- CIPN-20
- CIPN-R-ODS
- BPI
- Multidimensional Assessment of Interoceptive Awareness (MAIA-2)

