Functional MRI quantification: Volume and Surface preprocessing pipelines from the Human Connectome Project will be executed for each resting sequence on completion of structural preprocessing. MultiEcho ICA Cleaning: All resting state data will additionally be processed using MultiEcho ICA pipeline (AFNI) allowing removal of non-neural components in the BOLD data. Head motion: Rigorous control of head motion begins before acquisition with subject training and instruction, continues during scanning with repeated reminders to hold still and analysis of image quality after each scan with repetition as possible, and postprocessing including voxelwise despiking, motion parameter estimation and correction, physiologic waveform regression, Multiecho ICA cleaning, and volume censoring (scrubbing). Post-hoc mean and maximal root-mean-square head motion estimates will be used as covariates for all biomarkers. Connectivity: Time series will be estimated FreeSurfer-defined subject-specific regions of interest in somatosensory cortex, anterior cingulate, anterior insula, amygdala, thalamus, medial prefrontal cortex, orbitofrontal cortex, and precuneus, as well as at 361 ROIs for graph-theoretic and network analyses (modularity and clustering coefficient) comprising 333 cortical ROIs strategically positioned at network hubs, 14 cerebellar ROIs, and 14 subcortical gray matter ROIs defined from Freesurfer segmented subject specific nuclei.

Functional MRI Analysis: We will analyze functional connectivity using a parcellation covering the cortical and subcortical gray matter at 5 mm resolution. Brain parcellation will be constructed by assessing regions of interest (ROIs) and measuring each voxel, which can represent a million brain cells. Each voxel will be tested in sequence beginning with the inferior left voxel in the cerebellum. If a voxel is greater than 5 mm distant to voxels already selected, then this voxel will be included in the set of ROI center coordinates.

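### The planned connectivity analysis runs on a whole-brain 5 mm grid with no stated test or error control, while the plan's own three-region hypothesis is left without an analysis

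*Combined protocol and SAP*

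**What the plan says.** Section 12 (Statistical Considerations) describes three sets of brain regions.

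- **Named regions.** Under Functional MRI quantification, time series are estimated in FreeSurfer-defined "regions of interest in somatosensory cortex, anterior cingulate, anterior insula, amygdala, thalamus, medial prefrontal cortex, orbitofrontal cortex, and precuneus". That is eight regions. No analysis of these series is stated.
- **Network set.** The same paragraph adds a second set for a stated purpose: "as well as at 361 ROIs for graph-theoretic and network analyses (modularity and clustering coefficient) comprising 333 cortical ROIs strategically positioned at network hubs", plus 14 cerebellar and 14 subcortical regions.
- **5 mm grid.** Under Functional MRI Analysis the connectivity analysis is placed on a third set: "We will analyze functional connectivity using a parcellation covering the cortical and subcortical gray matter at 5 mm resolution". Its centres are chosen by stepping through voxels from a fixed starting point: "If a voxel is greater than 5 mm distant to voxels already selected, then this voxel will be included in the set". The number of regions is not given. Nor is it said whether the grid is built once or separately for each scan.

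The only modelling detail for fMRI is head motion as a covariate. The only significance level is in the Study Summary, and it belongs to the questionnaires: "group pre/post analysis with student t-test and chi square with significance will be set at .05 and two-tailed hypotheses".

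Section 2 (Background) predicts decreased connectivity between the insula, amygdala and somatosensory cortex when pain treatment succeeds. Section 1.2.1 makes cortical connectivity a secondary objective. On numbers, Section 4.3 says "Sample size for this pilot feasibility study is determined by budgetary constraints", and the retention target is "70% or more participants comply with 8 or more AT sessions and complete both fMRI scans".

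**The concern.** The one paragraph that says how connectivity will be analysed chooses the largest region set, for which a sample of 20 is least suited. It does not say how a change from first to second scan will be tested or how error will be controlled over the resulting comparisons. The smaller set that contains the hypothesised regions is extracted and then not used.

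The grid rule is also incomplete. Sequential selection depends on the mask and on the starting voxel. If it were run afresh for each scan, region *k* before treatment need not be region *k* after it, and a paired comparison of connections would be undefined.

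What is at stake is the mechanism question. It is in the trial's title and in a secondary objective, and Section 2 presents the pilot as groundwork for a randomised trial. If the region set, contrast and threshold are chosen after the data are seen, chance connections could become the mechanism hypotheses of that trial.

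**Working it through.** **The plan's own figure.** 333 + 14 + 14 = 361, so the count of the network set is right. The sample size rests on budget, so there is no power figure to reproduce.

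**Number of scan pairs.** At most 20. At the retention target, 0.70 × 20 = 14.

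**Size of the grid.** The documents give neither voxel size nor gray matter volume, so both are assumed. The sequential more-than-5-mm rule was run on 60 mm and 90 mm test cubes:

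| Voxel (mm) | mm³ per region, 60 mm cube | mm³ per region, 90 mm cube |
|---|---|---|
| 1 | 115 | 119 |
| 2 | 174 | 183 |
| 2.5 | 174 | 179 |
| 3 | 108 | 108 |

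The range is 108-183 mm³ per region. With 500-900 mL of gray matter:

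- Low: 500,000 / 182.6 ≈ 2,739 regions; 2,739 × 2,738 / 2 ≈ 3.7 million pairs.
- Middle: 700,000 / 115.1 ≈ 6,082 regions; 6,082 × 6,081 / 2 ≈ 18.5 million pairs.
- High: 900,000 / 108 ≈ 8,333 regions; 8,333 × 8,332 / 2 ≈ 34.7 million pairs.

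**If every pair were tested at an unadjusted two-sided 0.05.** The expected number of false positives when nothing changes is 0.05 × pairs, about 0.19 million (low) to 1.7 million (high). This expectation does not require independence. The plan does not state that such testing will be done.

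**If Bonferroni control were used.** For a paired t-test on *n* scan pairs, power is P(|T| > t at 1 − α/2), where T is noncentral t with *n* − 1 degrees of freedom and noncentrality d√n, and α = 0.05 / m for m pairs. Solving for 80% power gives the smallest detectable standardised change d:

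| Family | m | α per test | d, n = 20 | d, n = 14 |
|---|---|---|---|---|
| Three hypothesised pairs | 3 | 0.0167 | 0.78 | 0.97 |
| All pairs of the eight named regions (8 × 7 / 2) | 28 | 0.0018 | 1.02 | 1.31 |
| Grid, low | 3.7 million | 1.3 × 10⁻⁸ | 2.42 | 3.85 |
| Grid, middle | 18.5 million | 2.7 × 10⁻⁹ | 2.67 | 4.38 |
| Grid, high | 34.7 million | 1.4 × 10⁻⁹ | 2.77 | 4.60 |

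The value 0.97 is 0.975 before rounding. The calculation leaves out the few degrees of freedom that the head-motion covariates would use. The families of 3 and 28 take one region per name. Splitting the hypothesised regions by side gives 3 × 2 × 2 = 12 cross-region pairs, α = 0.05 / 12 = 0.0042, and d of 0.93 (n = 20) or 1.18 (n = 14).

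**The case against.** The strongest reply is that this is a secondary, exploratory aim in a feasibility pilot. The documents speak of potential mechanisms and preliminary data, and no feasibility decision depends on a connectivity result. That stands, and it limits the weight of the point. It does not supply the missing contrast or error control.

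Three stronger readings are tempting, and the documents do not support them.

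- *Chance connections will be reported as mechanisms.* This needs an unadjusted edgewise test. The plan states no fMRI test at all, and the 0.05 level is given for questionnaires. The false-positive counts above are therefore conditional.
- *The 361 regions give 361 × 360 / 2 = 64,980 tests and 3,249 false positives.* Section 12 assigns that set to modularity and clustering coefficient, which are network summaries. It does not plan tests of every pair.
- *The region sets contradict each other.* Different sets for different purposes are legitimate, and planning connectivity on the grid implies taking signals from it. The gap is narrower: the named regions have no stated analysis, and the hypothesis that needs them is not tested.

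It is also fair to say that Bonferroni is not the only correction. Permutation, false-discovery-rate or network-level methods would lose less, so the grid values of d are a guide to scale and do not prove that no mechanism can be found. Finally, the grid count is derived from assumed inputs, although thousands of regions result over the whole assumed range.

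**Conclusion.** The point holds and should be acted on. The stated connectivity analysis is poorly matched to at most 20 scan pairs. Under Bonferroni control the detectable change is about 2.7 (20 pairs) or 4.4 (14 pairs) on the middle grid, roughly three and a half to four and a half times the 0.78 or 0.97 for the hypothesis in Section 2. The regions needed for that hypothesis are already being extracted. Even those smaller values are large, so the pilot can support only a strong signal or an estimate with its interval.

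The grid figures rest on the assumed voxel sizes (1-3 mm) and gray matter volume (500-900 mL). The absence of a pre/post fMRI test, threshold and error control, and of any analysis of the named-region series, rests on no assumption. The primary feasibility endpoints are not affected, because fMRI enters them only as scan completion.

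**What to change.** Amend the fMRI part of Section 12 as follows.

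1. **Main contrasts.** Name the three Section 2 pairs (insula-amygdala, insula-somatosensory, amygdala-somatosensory), using the FreeSurfer series already extracted. State that the extracted anterior insula stands for the insula, if that is intended. Average the two sides, or enlarge the family if hemispheres are kept separate.
2. **Model and error control.** Specify a paired pre/post model with the planned head-motion covariates, and max-statistic permutation or Holm control over the family. Report estimates with intervals.
3. **Other named-region pairs.** Treat as secondary, with false-discovery-rate control.
4. **361-region set.** Keep for modularity and clustering, as already planned.
5. **5 mm grid.** Build once in template space, reuse for every scan, and report as exploratory with family-wise or network-level permutation correction.

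The cost is plan wording and standard permutation code, with no extra scans or participants. The downside is that fewer whole-brain results can be called findings.

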13 REGISTRATION GUIDELINES N/A

Patients must meet all of the eligibility requirements listed in Section 5 prior to study procedures.

14 DATA SUBMISSION SCHEDULE N/A

15 SPECIAL INSTRUCTIONS

15.1 **Pathology review** N/A

15.2 **Pharmacokinetic** N/A

15.3 Correlative Studies N/A

16 ETHICAL AND REGULATORY CONSIDERATIONS

16.1 Informed consent

Informed consent will be obtained from all research participants prior to performing any study procedures using the most recent Institutional Review Board (IRB) approved version.

16.2 Institutional Review

Study will be approved by the IRB of University of Utah.

16.3 Data and Safety Monitoring Plan

A Data and Safety Monitoring Committee (DSMC) is established at Huntsman Cancer Institute (HCI) and approved by the NCI to assure the well-being of patients enrolled on Investigator Initiated Trials that do not have an outside monitoring review. Roles and responsibilities of the DSMC are set forth in the NCI approved plan. The activities of this committee include a quarterly review of adverse events including SAEs, important medical events, significant revisions or amendments to the protocol, and approval of cohort/dose escalations. If the DSMC and/or the PI have concerns about unexpected safety issues, the study will be stopped and will not be resumed until the issues are resolved. The DSMC also reviews and approves audit reports generated by the Research Compliance Office.

This study is a low risk trial. All low risk studies are audited no less than annually by the Research Compliance Office and audit reports will be reviewed and approved by the full DSMC. The DSMC will also review all reportable Serious Adverse Events for patients on this study.

16.4 Adverse Events / Serious Adverse Events

This study will utilize the CTCAE (NCI Common Terminology Criteria for Adverse Events) Version 5.0 for AE and SAE reporting. An electronic copy can be downloaded from: https://ctep.cancer.gov/protocoldevelopment/electronic_applications/docs/CTCAE_v5_Quick_Reference_8.5x11.pdf

16.4.1 Adverse Events (AE)

There is no protocol-directed administration of systemic therapy in this nonpharmacologic study; patients will be taking standard of care anti-cancer therapy prescribed by their treating oncologist. The study-specific AE reporting plan detailed below will be followed. The PI will determine the attribution/relatedness of each AE. Any AEs with a *causal* relation to the research will be graded for severity and seriousness, and followed to either resolution or until the 3-month post follow-up (whichever comes first).

Subjects will receive a systemic treatment regimen for their cancer during study participation. Since such routine interventions and treatment may influence the study results, information regarding the concomitant medications will be collected but not reported to the IRB.

Potential AEs of acupuncture treatment include:

- Excessive and/or unusual bruising
- Excessive and/or unusual bleeding
- Needle shock
- Pre-syncope (Dizziness)
- Diaphoresis (Sweating)
- Nausea and Vomiting

Loss of consciousness

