All of these abbreviations may or may not be used in protocol.

PROTOCOL SIGNATURE

I confirm that I have read this protocol, and I will conduct the study as outlined herein and according to the ethical principles stated in the latest version of the Declaration of Helsinki, the applicable ICH guidelines for good clinical practice, and the applicable laws and regulations of the federal government.

I will provide copies of the protocol and all pertinent information to all individuals responsible to me who assist in the conduct of this study. I will discuss this material with them to ensure that they are fully informed regarding the study treatment, the conduct of the study, and the obligations of confidentiality.

Signature of Principal Investigator

12/3/2019 Date

[name] PhD, MAcOM, LAc Principal Investigator Name

College of Nursing, University of Utah Name of Institution

STUDY SUMMARY

Title	Acupuncture Treatment of Chemotherapy-
	Induced Peripheral Neuropathy (CIPN) in
	Women with Breast or Gynecologic
	Cancers: Feasibility and Mechanisms of
	Action
Short Title	CIPN Acu
Protocol Number	N/A
Phase	Clinical study phase: pilot phase II study
Design	Single arm, pilot feasibility study
Study Duration	18 months
Study Center(s)	Single-center: HCI/HCH
Objectives	This pilot study aims to demonstrate
	feasibility to recruit, retain and provide the
	study intervention and to identify potential
	mechanisms of action of acupuncture in
	CIPN management.
Number of Subjects	N=20
Diagnosis and Main Eligibility Criteria	This study will enroll female patients who
	have completed paclitaxel or docetaxel
	treatment at least 3 months prior with at
	least one month of altered sensation in feet
	(with or without presence in one or both
	hands) and/or pain with a score of greater
	than or equal to 20 for CIPN on the
	sensory subscale of the CIPN-20.
	Enrollment will be limited to patients with
	breast, ovarian, cervical, endometrial, or
	uterine cancer with CIPN and completed
	paclitaxel or docetaxel treatments.
Statistical Methodology	Primary Endpoints: Mean monthly
	enrollment, percentage completion rate of
	all study procedures, frequency count of
	serious adverse events, and percentage of
	enrolled participants completing
	questionnaires will be calculated. Data
	will be collected via REDCap and
	analyzed with SPSS.
	Analysis of demographic data will consist
	of calculating means standard deviations
	frequencies and proportions. Analysis of

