1 OBJECTIVES

This pilot study aims to evaluate the feasibility to conduct a study of acupuncture treatment (AT) for Chemotherapy-Induced Peripheral Neuropathy (CIPN) at Huntsman Cancer Institute and to investigate changes in physiological biomarkers when using acupuncture to treat CIPN.

1.1 **Primary Objectives and Endpoints**

To evaluate the feasibility to conduct a trial of AT for CIPN + standard of care therapy. Primary feasibility objectives will be evaluated in terms of recruitment (enrollment of 20 women, average of 2 eligible women per month to participate in the trial, identification of appropriate recruitment strategies, the appropriateness of eligibility criteria), retention (70% or more participants comply with 8 or more AT sessions and complete both fMRI scans), safety (zero serious adverse events directly related to AT) and questionnaire completion (70% or more enrolled participants comply with all data collection).

1.1.1 Primary outcome measures: Mean enrollment, completion rate of AT, fMRI, rate of serious adverse events, rate of questionnaire completion.

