Clinical data including current medications and medical history and fall rates will be gathered. Questionnaires (BPI, CIPN-20, CIPN-R-ODS, MAIA-2, Demograhpics) will be completed in person or emailed to patients via REDCap. Reminder calls and AT appointments will be scheduled by HCI Wellness and Integrative Health Center personnel in conjunction with a SC. The SC will aid participants in scheduling fMRI appointments online. AT treatments will occur within 7 days/4 business days in general. If participant prefers the first study fMRI and first AT appointment can occur same day, with the fMRI procedure occurring prior to AT treatment.

Follow up Visits:

Participants will receive 10 sessions of AT: twice per week for 2 weeks, thereafter once per week for six weeks, with a total of 10 treatments during a two-month course. Each session will last 45-60 minutes, with acupuncture needles retained 30-40 minutes. A minimum of 8 treatments must be received by each participant with no more than 9 days' gap between weekly treatments permitted (sessions 5-10). Concurrent medications are allowed as prescribed and will be tracked in the study and analyzed as potential confounders.

Final Visit:

Participants will undergo examination within one week of AT completion. This will include the fMRI scan and questionnaires. Compensation for participation will be offered at this visit.

Procedures:

Measures: Questionnaires will be completed in person or emailed to patients via REDCap at baseline and study conclusion, as well as at a 3-month follow-up. *Primary Endpoints:* Mean enrollment, percentage completion rate of all study procedures, frequency count of serious adverse events, and percentage of enrolled participants completing questionnaires will be calculated. Data will be collected via REDCap, stored in the Research Subject Registry (RSR) and analyzed with SPSS.

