11.2 Safety

The DSMC will consist of the appropriate Huntsman Cancer Institute (HCI) DSMC members.

Overall safety of this study will be assessed using the CTCAE (NCI Common Terminology Criteria for Adverse Events) version 5.0 and the following safety and tolerability endpoints will be used:

-incidence of treatment-emergent adverse events associated (TEAE's) with acupuncture- known TEAE's detailed below.

Patients will be instructed to disclose all study-related side-effects, symptoms or AEs. Potential adverse effects of acupuncture treatment include: Bruising Bleeding Needle shock Pre-syncope (Dizziness) Diaphoresis (Sweating) Nausea and Vomiting Loss of consciousness

The main side effects of acupuncture include a slightly increased risk of minor bruising and bleeding and rarely infection. Needle shock, a vaso-vagal response to needle insertion, occurs about 5% of the time usually during the first or second treatment. Patients may become faint, diaphoretic, nauseated and occasionally lose consciousness. These are often reversible by removing the acupuncture needles and laying the patient supine.

-incidence of procedure-related adverse events associated with fMRI (source: FDA)

MR images are made without using any ionizing radiation, so patients are not exposed to the harmful effects of ionizing radiation. But while there are no known health hazards from temporary exposure to the MR environment, the MR environment involves a strong, static magnetic field, a magnetic field that changes with time (pulsed gradient field), and radiofrequency energy, each of which carry specific safety concerns:

• The strong, static magnetic field will attract magnetic objects (from small items such as keys and cell phones, to large, heavy items such as oxygen tanks and floor buffers) and may cause damage to the scanner or injury to the patient or medical professionals if those objects

become projectiles. Careful screening of people and objects entering the MR environment is critical to ensure nothing enters the magnet area that may become a projectile.

- The magnetic fields that change with time create loud knocking noises which may harm hearing if adequate ear protection is not used. They may also cause peripheral muscle or nerve stimulation that may feel like a twitching sensation.
- The radiofrequency energy used during the MRI scan could lead to heating of the body. The potential for heating is greater during long MRI examinations.

Acupuncture Schedule Adjustments

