16.5 SAE Reporting Requirements

SAEs must be reported to the DSMC and/or the IRB according to the requirements described below:

DSMC Notifications:

- All SAEs which are attributable to study intervention will be reported to the DSMC.
- A MedWatch 3500A form* must be completed and submitted to [contact] as soon as possible, but no later than 24 hours from first knowledge.
- An HCI Research Compliance Officer (RCO) will process and submit the MedWatch form to the proper DSMC member as necessary for each individual study.
- The RCO will summarize and present all reported SAEs according to the Data and Safety Monitoring Plan at the quarterly DSMC meeting.

IRB Notification:

• Events meeting the University of Utah IRB reporting requirements (http://www.research.utah.edu/irb/) will be submitted through the IRB's electronic reporting system within 10 working days.

*Medwatch 3500A form can be found at

http://www.fda.gov/downloads/Safety/MedWatch/HowToReport/DownloadForms/ucm0827 28.pdf

16.6 **Reporting of Pregnancy**

Although pregnancy is not considered an adverse event, it is the responsibility of investigators or their designees to report any pregnancy or lactation in a subject as an SAE. Pregnancies or lactation that occurs during the course of the trial or with 30 days of completing the trial or starting another new anticancer therapy, whichever is earlier, must be

reported to the DSMC, and IRB. All subjects and female partners who become pregnant must be followed to the completion/termination of the pregnancy. Pregnancy outcomes of spontaneous abortion, missed abortion, fetal death, intrauterine death, miscarriage and stillbirth must be reported as serious events.

16.7 **Protocol Amendments**

Any amendments or administrative changes in the research protocol during the period, for which the IRB approval has already been given, will not be initiated without submission of an amendment for IRB review and approval.

These requirements for approval will in no way prevent any immediate action from being taken by the investigator in the interests of preserving the safety of all patients included in the trial.

16.8 **Protocol Deviations**

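### The plan provides for seriousness grading and DSMC notification only where the PI finds a causal link, so the unqualified SAE count is not assured and 'unrelated' rulings are not routinely seen

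*Combined protocol and SAP*

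**What the plan says.** **Endpoint.** Section 10 (Procedures, Primary Endpoints) lists a "frequency count of serious adverse events" with no relatedness limit, and the Study Summary does the same. Section 1.1.1 gives the primary outcomes as "Mean enrollment, completion rate of AT, fMRI, rate of serious adverse events, rate of questionnaire completion", and Section 11.1 has a near-identical list. The success criterion in Sections 1.1, 11.1 and 12 is narrower: no SAE directly related to acupuncture treatment (AT). Section 11.2 adds the incidence of treatment-emergent events associated with acupuncture.

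**Collection and grading.** Section 11.2: "Patients will be instructed to disclose all study-related side-effects, symptoms or AEs". Section 16.4.1: "The PI will determine the attribution/relatedness of each AE". The same section then says that events with a causal "relation to the research will be graded for severity and seriousness".

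**Reporting.** Section 16.4.2 sends on events that the PI finds both attributable and serious. Section 16.5: "All SAEs which are attributable to study intervention will be reported to the DSMC". Section 16.3 gives the DSMC a general quarterly review of adverse events, but its sentence about this particular study refers to reportable SAEs.

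**The concern.** The endpoint and the process behind it do not match. Two places promise a count of SAEs without qualification. The process described is filtered on relatedness at three points: what the patient is asked to mention, what is graded for seriousness, and what the DSMC is sent.

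Two things are at stake. A reader of the results could take the SAE count as all-cause when it may not be. And the primary safety criterion depends on a relatedness judgement made by one person who knows the treatment. When that judgement is 'unrelated', the plan does not routinely put the event before the one committee set up to look at safety.

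Attribution is unlikely to be easy here. Section 16.4.1 says participants receive cancer treatment during the study. Section 2 links neuropathy to gait instability and falls. Section 11.2 lists dizziness and loss of consciousness among the possible effects of acupuncture. A fall leading to hospital admission could be put down to any of the three.

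**Working it through.** **1. Is there a figure to reproduce?** No. The criterion is a threshold of 0 related SAEs among 20 women. On the 20, Section 4.3 says: "Sample size for this pilot feasibility study is determined by budgetary constraints". No error rate, power, assumed SAE rate or precision is attached to the criterion.

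**2. What the process delivers for each stated quantity.**

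| Quantity | Where stated | Deliverable from the process described? |
|---|---|---|
| SAE count, no relatedness limit | Summary, Section 10 | Not assured: no provision has an event ruled unrelated graded for seriousness |
| SAE rate, no relatedness limit | 1.1.1, 11.1 | Same if read literally; may be shorthand for the row below |
| AT-related SAE count | 1.1, 11.1, 12 | Yes, subject to disclosure and to the PI's attribution |
| Acupuncture-associated TEAE incidence | 11.2 | Yes, on the same condition |

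**3. Does the order of the two judgements matter to the criterion?** The criterion counts events that are related and serious. Grading seriousness first and relatedness second, or the reverse, gives the same set. The order alone therefore does not bias the related-SAE count. What can change it is a related event that is never disclosed, or one that is wrongly ruled unrelated.

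**4. How sensitive is the criterion to that?** Let p be the true risk per woman of an AT-related SAE, and m the share of such events that are ruled unrelated. Neither is in the documents; both are assumptions shown over a range. With 20 women observed:

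P(criterion met) = (1 − p(1 − m))^20

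| p | m = 0 | m = 25% | m = 50% | m = 75% |
|---|---|---|---|---|
| 2% | 66.8% | 73.9% | 81.8% | 90.5% |
| 5% | 35.8% | 46.6% | 60.3% | 77.8% |
| 10% | 12.2% | 21.0% | 35.8% | 60.3% |

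For example, p = 5% and m = 50% gives (1 − 0.05 × 0.5)^20 = 0.975^20 = 0.603, against 0.95^20 = 0.358 with perfect attribution. The same formula applies if m is read as the share never disclosed.

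**5. What a clean result would support.** With 0 of 20, the exact one-sided 95% upper limit is 1 − 0.05^(1/20) = 13.9%, and the two-sided limit is 1 − 0.025^(1/20) = 16.8%. Both presume that every related SAE was found and correctly attributed.

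**The case against.** The case for leaving the text alone has several parts.

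- **The endpoint is defined.** In Sections 1.1 and 11.1 the short outcome list directly follows the related-SAE definition, so it is natural to read it as shorthand, and Section 12 uses the related count. This stands for those sections. It does not help the Summary or Section 10, where no such definition is nearby.
- **Section 16.4.1 does not say 'only'.** True. It says causal events will be graded and is silent on the rest, while Sections 8, 11.2 and 16.4 apply CTCAE without a relatedness limit. That is why the count is described here as not assured rather than as impossible.
- **There are other routes and checks.** Section 11.2 has staff act on any problem they detect, and its telephone route has no relatedness limit for AEs. Pregnancy and lactation bypass attribution (16.6). Section 16.3 provides audits at least annually, and IRB reporting follows the IRB's own requirements (16.5). All of this stands. None of it provides for grading an SAE ruled unrelated or listing it for the DSMC.
- **Open-label attribution is inherent in the design.** The Summary describes a "Single arm, pilot feasibility study", and Section 16.3 calls it low risk. This also stands, but it is a reason to make the attribution visible, since it cannot be masked.

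A reader might go further and infer that the safety endpoints cannot be produced, that grading after attribution pushes the count towards zero, or that the only independent check has been removed. The documents support none of these: the related counts can be computed, the order does not change them, and audits and IRB rules are further checks. Nor does an assumed all-cause SAE rate size the problem, because leaving out unrelated events does not alter the related count.

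**Conclusion.** The point holds in a limited form. The unqualified SAE count in the Summary and Section 10 is not assured as an all-cause figure. The zero-SAE criterion and the TEAE incidence can be evaluated, but they rest on patients judging relatedness for themselves and on one open-label PI decision, with no second assessor named and no routine DSMC sight of an 'unrelated' ruling. The risk is under-ascertainment and unchecked misattribution.

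No stated number in the plan is wrong, and no misattribution has been shown. The table in the working indicates only how far the criterion could be affected. Over assumed related-SAE risks of 2% to 10%, missing half of related events raises the chance of meeting it by between 15.0 percentage points (66.8% to 81.8%, at 2%) and 24.5 points (35.8% to 60.3%, at 5%), with 23.6 points at 10% (12.2% to 35.8%). These rest wholly on the assumed p and m. This is a cheap improvement to a primary safety outcome, not a defect that undermines the pilot.

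**What to change.** - **Sections 16.4.1, 16.4.2 and 16.5:** record and grade every SAE from the first study procedure to week 22 whatever its attribution, and hold attribution as a separate field. List all SAEs, with the PI's attribution, at the quarterly DSMC review that already exists.
- **Section 11.2:** ask women to report any new or worsening symptom, so that they are not asked to decide relatedness themselves.
- **Section 12:** report two counts, all SAEs and SAEs directly related to AT. Keep the second as the zero-SAE criterion, unchanged. Align the wording in the Summary, 1.1.1, 10 and 11.1 with this.

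This does not remove the possibility of misattribution, and it adds no second assessor; it lets the DSMC see each ruling. The cost is protocol wording and slightly more adverse event recording in 20 women, with no extra staff.
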